#### 5. STUDY POPULATION

The EpiNet-First trials will be conducted in people with new onset epilepsy, who have never been treated with anti-epileptic drugs for more than one week. Separate trials will be run for patients with focal seizures, generalised seizures, and seizures whose nature is uncertain. Altogether, 1467 patients with focal onset seizures, 1170 patients with generalised onset seizures, and 1840 patients with seizures of uncertain nature will be recruited.

#### 5.1 Inclusion Criteria

Patients with the following characteristics will be eligible for inclusion in the trial:

- a) Aged 5 years or older on date of consent;
- b) The investigator is confident that the patient has epilepsy (at least an 80% level of confidence);
- c) Two or more spontaneous seizures that require antiepileptic drug treatment (focal or generalized, provided all seizures have not been absence seizures);
- d) Antiepileptic drug monotherapy considered the most appropriate option, and each of the AEDs for the particular trial considered by the investigator to be appropriate;
- e) Willing to provide consent. For patients younger than the age of consent (usually 16 years), patient's parent/legal representative willing to give consent, and the patient willing to give assent (details depending on country-specific requirements)

#### 5.2 Exclusion Criteria

Patients with the following characteristics will be excluded from the trial:

- a) Seizures provoked by alcohol or recreational drugs;
- b) Acute symptomatic seizures (e.g. acute brain haemorrhage or brain injury);
- c) Only absence seizures;
- d) Is thought to have psychogenic non-epileptogenic seizures
- e) Has ever been treated with an antiepileptic for more than one week;
- f) Known progressive neurological disease (e.g. known brain tumour).

# 5.3 Cessation/Change of AED Treatment, Patient Transfer and Withdrawal

In consenting to the trial, patients are consenting to trial treatment, follow-up and data collection. If withdrawal of the randomly allocated treatment occurs, patients should still be followed up to allow a thorough assessment of the treatment policies, as patients may still achieve the primary outcome (12 month remission) following withdrawal of randomised treatment.

# 5.3.1 Cessation/Change of AED Treatment

If withdrawal of the randomly allocated treatment occurs (either due adverse events or insufficient efficacy), or additional AEDs are added to the randomly allocated treatment patients should still be followed up to allow a thorough assessment of the treatment policies, as patients may still achieve the primary outcome (12 month remission) following withdrawal of randomised treatment.

#### 5.3.2 Patient Transfers

For patients moving from the area, every effort should be made for the patient to be followed-up at another participating trial centre and for this trial centre to take over responsibility for the patient.

A copy of the participant's EpiNet record will be attached to the cohort of the investigator at the new site. The patient (or parent / legal representative) will have to sign a new consent form at the new site, and until this occurs, the patient remains the responsibility of the original centre.

# **5.3.3 Withdrawal from Trial Completely**

Patients (or patients parent / legal representative where the patient is aged under 16 years of age) are free to withdraw consent at any time without providing a reason. Patients who wish to withdraw consent to participate in the trial will have anonymised data collected up to the point of that withdrawal of consent included in the analyses. The patient will not contribute further data to the study. A consent withdrawal form should be completed-and the reason for trial withdrawal should be recorded in the EpiNet record. Data up to the time of withdrawal will be included in the analyses unless the patient explicitly states that this is not their wish.

#### 6. ENROLMENT AND RANDOMISATION

# 6.1 Screening

All patients aged 5 years and over, who have had two or more spontaneous seizures that require antiepileptic drug treatment, and have not been treated with any antiepileptic drug for more than one week will be screened at the study centres to identify potentially eligible participants for the study. These patients will all have records created in the EpiNet database. Investigators will be encouraged to record data prospectively in the First-AED registry within EpiNet, even if the patients are not included in any of the EpiNet-First trials. Reasons for non-participation will be recorded. Reasons for declining to participate will be asked routinely but it will be made clear that patients, parents or carers do not have to provide a reason unless happy to do so.

Potentially eligible patients (i.e. those that meet the eligibility criteria listed in section 5) or their parent / legally acceptable representative where appropriate, will be invited to participate in the study and provided with a patient information sheet and consent form. The patient (or parent / legally acceptable representative where appropriate) will be allowed sufficient time to discuss the trial and decide whether to consent to trial entry (see section 11.3 for consent procedures). Children who are old enough to read and understand the concepts relating to a clinical trial will be offered a separate assent form.

# 6.2 Baseline

Once consent has been obtained from the patient (or parent / legal representative where applicable, and assent by the child where appropriate and applicable) the delegated member of the research team e.g. research nurse/consultant should record the required baseline data (which will include seizure history, history of neurological insult, febrile seizures, family history of epilepsy, EEG and imaging (CT or MRI) results) into the EpiNet record. If further investigations (EEG or imaging) are requested at this visit, data on results will be collected when available, but randomisation need not be delayed. If the patient is confirmed eligible then the research team should proceed to randomise the patient.

#### 6.3 Randomisation

Patients **should not** be randomised until:

- a) Consent has been obtained from the patient (parent / legal representative where the patient is under 16 years of age)
- b) The minimum baseline data has been recorded into the EpiNet record;
- c) Eligibility criteria have been fulfilled.

The trial in which the patient will be enrolled will be determined by the seizure type and the willingness of the patient to take valproate. Investigators will be guided through this process by algorithms within the EpiNet database. Investigators will be asked what type of seizures the patient has, and whether the patient would be willing to take valproate. Patients will then be randomised to one of the following treatments:

For each of the trials, randomisation will be by block randomisation with variable block size to minimize any potential for predicting allocation. Randomisation will be stratified by country, age (below 18 vs 18 or older) and sex.

Patients who have focal seizures will be entered into the **EpiNet-First Trial 1**, and randomised to receive either levetiracetam or lamotrigine or carbamazepine (in a 1:1:1 ratio).

Patients who have generalised seizures (excluding patients who have a focal onset to their seizures, or who have absence seizures alone) who are willing to take valproate will be entered into the **EpiNet-First Trial 2** and randomised to receive either levetiracetam or valproate (in a 1:1 ratio),

Patients who have generalised seizures (excluding patients who have a focal onset to their seizures, or who have absence seizures alone) who are NOT willing to take valproate will be entered into the **EpiNet-First Trial 3** and randomised to receive either levetiracetam or lamotrigine (in a 1:1 ratio)

Patients who have seizures of uncertain nature who are willing to take valproate will be entered into the **EpiNet-First Trial 4** and randomised to receive either levetiracetam or lamotrigine or valproate (in a 1:1:1 ratio).

Patients who have seizures of uncertain nature who are NOT willing to take valproate will be entered into the **EpiNet-First Trial 5** and randomised to receive either levetiracetam or lamotrigine (in a 1:1 ratio).

Participants will be randomised from within the EpiNet database, using a secure (24-hour) web based randomisation programme. Personal login username and password will be required to access the EpiNet database and the web-based randomisation system. When eligibility has been confirmed the participant will be randomised. Treatment allocation will be displayed to the authorised randomiser on a secure webpage within the EpiNet record, and an automated email confirmation will be sent to the authorised EpiNet investigator, PI and the trial coordinator.

If there are any problems with the randomisation systems, please contact the EpiNet-First coordination service via e-mail: [contact]

#### 7. TRIAL TREATMENTS

#### 7.1 Introduction

EpiNet-*First* comprises five randomised controlled trials run in parallel. Depending on the specific trial, patients will be randomised to receive either levetiracetam, lamotrigine, carbamazepine or valproate.

Randomised treatment should begin within 7 days of randomisation. The research team should ensure that any delay before starting the trial treatment does not impact on the well-being of the participant. Assessments that should be carried out prior to the start of the randomised treatment are detailed in sections 6 and 8.

All treatments will be prescribed and issued as per routine practice. Generic versions of AEDs can be prescribed, if these are routinely used in a particular centre. Specific details regarding which version of an AED is used will be recorded.

If a patient has already been commenced on an AED, he can only be recruited for any of the EpiNet First trials if:

- he/she has taken the AED for 7 days or less;
- he/she agrees to be randomised to one of the treatment arms for the trial for which the patient is eligible. (In some circumstances, it may be possible for the patient to be randomised to the drug which he/she is already taking.)
- the investigator considers that it is appropriate to include the patient in the trial.

In these circumstances, if a patient is randomised to another AED, the original AED should be withdrawn according to the investigator's standard clinical practice. In most circumstances, since the patient will have used the drug for only a few days, it will be appropriate to discontinue the AED immediately. The new AED (to which the patient has been randomised) will be introduced according to routine clinical practice. If appropriate, the two drugs can be overlapped for a brief period. Full details including the dates on which the original AED was commenced and discontinued, and the dose used, should be recorded in the EpiNet record.

If a patient is randomised to the same AED that he / she was already taking, the drug should simply be continued and/or increased according to routine practice. The date on which the patient started the drug should be recorded in the EpiNet record, even if that date is earlier than the date of randomisation. Outcome data will be calculated from the date of randomisation.

Patients will be recruited over a 3.5 year period and follow up will continue for a further two years. Thus the maximum time that a patient will participate in any of the trials is 5.5 years.

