# 1 PROTOCOL SUMMARY

Title:	A series of 5 pragmatic randomised controlled trials comparing the effectiveness of levetiracetam, lamotrigine, carbamazepine and sodium valproate for previously untreated epilepsy: EpiNet- First trials
Phase:	IV
Population:	1467 patients with focal onset seizures, 1170 patients with generalised onset seizures, and 1840 patients with seizures of uncertain nature.
	Inclusion Criteria:  ☐ Aged 5 years or older on date of consent;  ☐ Confident diagnosis of epilepsy (at least 80% certainty)  ☐ Two or more spontaneous seizures that require antiepileptic drug treatment;  ☐ Antiepileptic drug monotherapy considered the most appropriate option;  ☐ Willing to provide consent (patient's parent/legal representative willing to give consent where the patient is aged under 16 years of age)
	Exclusion Criteria:  Provoked seizures (e.g. alcohol, recreational drugs);  Acute symptomatic seizures (e.g. acute brain haemorrhage or acute brain injury);  Only absence seizures;  Psychogenic non-epileptogenic seizures  Has ever been treated with an antiepileptic for more
Study Centres and Distribution:	Multinational study. Out-patient epilepsy, general neurology and paediatric (epilepsy and general) clinics
Study Duration:	Minimum participant duration 2 years  Maximum participant duration 5.5 years
Description of Agent/ Intervention:	All trial medication will be prescribed in a formulation and at a dose deemed suitable by the treating physicians

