# 2.3 Objectives

**EpiNet-First-Trial 1** - To determine whether levetiracetam is more effective than either lamotrigine or carbamazepine when used as monotherapy in patients with untreated focal-onset seizures.

**EpiNet-First Trial 2** - To determine whether levetiracetam is more effective than valproate in patients with untreated generalised-onset seizures. (Patients with absence seizures alone are not included.)

**EpiNet-First-Trial 3** — To determine whether levetiracetam is more effective than lamotrigine in patients with untreated generalised-onset seizures for whom valproate is not suitable. (Patients with absence seizures alone are not included.)

**EpiNet-First-Trial 4** - To determine whether levetiracetam is more effective than lamotrigine or valproate in patients with untreated seizures of uncertain nature.

**EpiNet-First-Trial 5** - To determine whether levetiracetam is more effective than lamotrigine in patients with untreated seizures of uncertain nature, for whom valproate is not suitable.

A full list of outcome measures is presented in section 4.

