## 9.6 Per-Protocol Analysis / Protocol Violations

Secondary per protocol (PP) analyses will be undertaken to assess the robustness of ITT analyses. Per protocol analyses will exclude patients who turned out not to have epilepsy, patients who were lost to follow up or for whom there is inadequate data to determine if they reached the primary endpoint, and all patients who took a different AED from the drug to which they had been randomised, before reaching the primary endpoint. Patients who were enrolled in EpiNet-First Trial 1 who turned out not to have focal seizures will be excluded from the PP analysis; similarly, patients who were enrolled in EpiNet-First Trial 2 or Trial 3 who turned out to have focal seizures (even if these evolved into generalised seizures) will also be excluded from the PP analysis. However, all patients who were included in EpiNet-First Trial 4 or Trial 5 will be included in the PP analysis if they had epilepsy, even if the exact nature of the seizures became clearer during the course of the trial.

The decision regarding which patients to exclude from the PP analysis will be made by the Trial Steering committee, who will be blinded to the treatment allocation and outcome data for each patient.

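### The per-protocol rule in 9.6 makes no exception for the drug changeover that 7.1 permits, so exclusion can depend on the allocated arm

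*Protocol*

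**What the plan says.** Section 7.1 allows entry to a patient already on treatment provided "he/she has taken the AED for 7 days or less". The limit agrees with the description of the population in section 5 ("never been treated with anti-epileptic drugs for more than one week") and with exclusion criterion 5.2(e) ("Has ever been treated with an antiepileptic for more than one week"). The title and objectives are worded more loosely: the title says "for previously untreated epilepsy", and the Trial 1 objective refers to treatment "when used as monotherapy in patients with untreated focal-onset seizures".

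Section 7.1 then gives two routes. It notes that "it may be possible for the patient to be randomised to the drug which he/she is already taking"; in that case the drug is continued or increased. If another drug is allocated, the first drug is withdrawn, in most cases at once, the new one is introduced, and a short overlap is acceptable. On both routes the clock is the same: "Outcome data will be calculated from the date of randomisation".

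Section 9.1 describes the per-protocol set as randomised patients who took the study drug and had no major violation. Section 9.6 lists the exclusions, among them "all patients who took a different AED from the drug to which they had been randomised, before reaching the primary endpoint". It says the analysis is there to test the robustness of the intention-to-treat (ITT) result. The Trial Steering Committee decides exclusions blinded to allocation and outcome.

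**The concern.** A patient who arrives on drug A and is allocated drug B has taken a drug other than B before reaching the endpoint, and has done exactly what 7.1 provides for. Nothing in 9.6 exempts this patient. The same patient allocated drug A would be retained. Whether a pre-exposed patient stays in the per-protocol set is then settled by the allocation, not by adherence.

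This undermines the purpose of the analysis. A per-protocol set that loses a different share of compliant patients from each arm is a poor check on ITT: if the two analyses differ, the cause may be the exclusion rule. Because the committee does not see allocation, it cannot easily tell a permitted changeover from an unplanned switch case by case, so the written rule has to make the distinction.

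Endpoint 4.2(g), which counts early remission only in patients who have not changed to a different AED, has the same gap. It does not say whether moving from the starter drug to the allocated drug is such a change.

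**Working it through.** **1. How each kind of patient fares under 7.1 and 9.6**

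| Patient at entry | Course under 7.1 | Position under 9.6 as written |
|---|---|---|
| No prior AED | starts allocated drug | kept |
| On drug A, allocated A | continues | kept |
| On drug A, allocated B, A stopped at randomisation | compliant switch | excluded on a literal reading; kept if only use after randomisation counts |
| On drug A, allocated B, with overlap | compliant switch | excluded on either reading |

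Rows 3 and 4 also satisfy the description in 9.1, so 9.1 and 9.6 disagree on them.

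**2. The plan's own figure**

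The only protocol figure needed is 489 per arm in Trial 1 (section 9.2), which is not disputed. It can be reproduced with Freedman's event formula, 67% v 77%, two-sided alpha 0.025, 90% power and 10% loss:
- HR = ln(0.23)/ln(0.33) = 1.326.
- Events = 3.523² × (2.326/0.326)² ≈ 633.
- Per arm = 633/0.72/2/0.9 ≈ 488 to 490, depending on rounding.

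Inputs of 70% v 60% at alpha 0.05 fit about as well, so the match does not show which inputs were used.

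**3. Exclusions in Trial 1 on the literal reading**

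Assumption: a share f = 10-30% of patients is pre-exposed. The protocol gives no figure.
- Pre-exposed per arm = 489 × f: 489 × 0.10 ≈ 49 and 489 × 0.30 ≈ 147.
- Everyone started on the same trial drug: 0 excluded in that drug's arm, and 2 × 49 = 98 to 2 × 147 = 294 across the other two. This is the upper bound on the imbalance for that range of f.
- Starters split 60/20/20 over the three trial drugs, f = 10%: 48.9 × 0.4 ≈ 20 excluded in the main starter's arm, 48.9 × 0.8 ≈ 39 in each of the others.
- Even split, f = 10%: 48.9 × 2/3 ≈ 33 in every arm, so no imbalance.
- Starter outside the trial drugs: every pre-exposed patient switches in every arm, so again no imbalance.

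On the narrower reading only overlaps count. Section 7.1 expects immediate discontinuation in most cases, so the numbers would be well below these, but overlap can still occur only in switchers.

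**4. Does the head start matter for the primary endpoint?**

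The lead is at most 7 days, or 7/365.25 = 1.9% of the 12-month remission period. Assume remission rises linearly from 20-50% at 12 months to 70% at 24 months; 7 days is 0.23 month.
- Shift at 24 months if the whole arm were pre-exposed: (70 − 20)/12 × 0.23 ≈ 0.96 points; (70 − 50)/12 × 0.23 ≈ 0.38 points.
- At f = 10%: 0.04-0.10 points. At f = 30%: 0.12-0.29 points. The design difference is 10 points.
- With about 440 evaluable per arm (489 × 0.9) at 70%, a bias of 0.1-0.3 points gives a two-sided rejection rate of 5.0-5.1% against the nominal 5%.

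**The case against.** A reader might go further and infer that the arm of the locally usual starter drug carries a head start and pre-screened tolerability that tilt the randomised comparison itself. The documents do not support that as a finding:
- The 7-day allowance is declared consistently in sections 5, 5.2, 6.1 and 7.1. The word untreated in the title and objectives is loose shorthand for a defined population.
- Exposure precedes randomisation, so the pre-exposed share is balanced in expectation and ITT is valid for the patients enrolled.
- Seven days falls inside the first two-week step of every recommended schedule in 7.3, although clinicians may vary titration. Other patients may themselves start up to 7 days after randomisation.
- No section says that early reactors go unentered, or how many there are. The inference rests on the requirement in 5.1(d) that each trial drug be judged appropriate. If 1-5% of starters were intolerant in the first week, treatment failure in that arm would fall by 0.1 points (10% × 1%) to 1.5 points (30% × 5%), and this is a secondary endpoint.
- Section 2.2 reports carbamazepine as a usual first choice in focal seizures and valproate as widely preferred in generalised seizures. That makes uneven starters plausible; it does not establish them.

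Against the narrower point, it can fairly be said that 9.6 is most naturally read as use after randomisation, that the per-protocol analysis is secondary, and that the committee is blinded. The first argument shrinks the problem without removing it, because overlap is use after randomisation. The second limits the severity. The third leaves the wording to decide.

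**Conclusion.** The point holds as a defect in a written rule, of minor severity. Section 9.6 does not exempt the changeover and overlap that 7.1 allows, so compliant switchers can be excluded while continuers are kept, and the exclusion follows allocation whenever starter drugs are unevenly distributed. The size is unknown. The 98-294 figure against none assumes a 10-30% pre-exposed share, a single starter drug that is one of the Trial 1 drugs, and the literal reading; relaxing the second or third assumption reduces it, to no imbalance when starters are evenly mixed or outside the trial drugs. The ITT primary analysis is not in question.

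**What to change.** In 9.6, state that an AED taken before randomisation, and its withdrawal or brief overlap as allowed in 7.1, does not count as taking a different AED. Apply the same reading to endpoint 4.2(g). Recruitment and the handling of patients under 7.1 stay as they are. The cost is a sentence in 9.6 and a cross-reference in 4.2(g).

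Optionally, repeat the primary endpoint and 4.2(a)-(d) in patients with no AED before randomisation. This subset is fixed at baseline, keeps the randomised comparison and matches the untreated wording of the objectives. It costs slightly less precision and no new data, since 7.1 already requires the start date of the earlier drug to be recorded. It could equally be placed in the statistical analysis plan, and its absence from the protocol is not a fault.

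Adding prior AED as a main-effect covariate is not a remedy: pre-exposure means continuing in one arm and switching in another, and a single common coefficient cannot represent that.
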